7.1.1 EMERGENCY TREATMENT & UNMASKING

In case of an emergency where knowledge of the patient's randomized treatment assignment is essential to the treatment of the patient, the investigator may willingly become unmasked. This decision to unmask resides solely with the investigator. If unmasking is warranted, the investigator will call their unmasked research pharmacist who can readily unmask the patient's treatment assignment. The research pharmacist must notify the Coordinating Center if they provide the treatment assignment to the masked investigator. If the research pharmacist is unable to be reached, the investigator may call the Coordinating Center. The Data Analyst is the best contact for this situation, as they are unmasked. Based on investigator discretion, the investigator should restrict the number of individuals who become unmasked. The patient should remain in the study, regardless of whether they have been unmasked, if the patient's safety is not at risk. As with any unmasking, the investigator must report a Protocol Deviation. See section 10.1.9 for further details on reporting Protocol Deviations.

7.2 PARTICIPANT DISCONTINUATION/WITHDRAWAL FROM THE STUDY

Participants are free to withdraw from participation in the study at any time upon request.

An investigator may discontinue or withdraw a participant from the study for the following reasons:

- Pregnancy
- Significant study intervention non-compliance that endangers the participant
- If any clinical AE, laboratory abnormality, or other medical condition or situation occurs such that continued participation in the study would not be in the best interest of the participant

The reason for participant discontinuation or withdrawal from the study will be recorded on **Patient Dropout Form**. Subjects who sign the ICF and are randomized but do not receive the study intervention must continue to be followed as part of the study and will be included in the intent-to-treat analysis. Subjects who sign the ICF, are randomized and receive the study intervention, and subsequently withdraw, or are withdrawn or discontinued from the study will not be replaced.

7.3 LOST TO FOLLOW-UP

The following actions must be taken if a participant fails to return to the clinic for a required study visit:

- The site will attempt to contact the participant and reschedule the missed visit and counsel the participant on the importance of maintaining the assigned visit schedule and ascertain if the participant wishes to continue in the study.
- The investigator or designee will make every effort to reestablish contact with the participant (where possible, three telephone calls and, if necessary, a certified letter to the participant's last known mailing address or local equivalent methods). These contact attempts should be documented in the participant's medical record or study file.
- Patients are not considered a dropout unless they state they are no longer willing to participate in the study. Study personnel should continue to reach out to the study patient in an effort to schedule a study visit until the end of the Month 12 visit window.

8 STUDY ASSESSMENTS AND PROCEDURES

8.1 EFFICACY ASSESSMENTS

Dilated ophthalmic exam: A study ophthalmologist at each site will be required to perform an eye examination at each study visit. This examination should be similar to that performed in the routine care of patients with uveitis. Several components will be assessed in detail per study protocol. Anterior chamber cell, anterior chamber flare, and vitreous haze will be graded based on Standardization of Uveitis Nomenclature (SUN) Working Group inflammation grading schemes.⁶⁰ The study ophthalmologist will also examine the fundus for any sign of retinal or choroidal inflammation and will record any abnormal findings on **Clinical Eye Exam Form**.

Rheumatologic exam: A pediatric rheumatologist will conduct an exam of joint disease activity at Baseline, Treatment Failure (if applicable) and Months 3, 6, and 12. These exams will occur on the same day as, or as close as possible to, the ophthalmic exam. This exam will include assessment of total active joint count, systemic symptoms such as fever or rash, and other tests or examinations deemed necessary by the rheumatologist. Juvenile Arthritis Disease Activity Score (JADAS) for 10 joints and 27 joints will be determined at each visit based on ESR, physical exam, and assessment of patient functioning.^{70,71} Findings will be recorded on **Arthritis Evaluation Form**.

Best spectacle-corrected visual acuity (BCVA): Trained visual acuity technicians will use the Electronic Visual Acuity (EVA) protocol developed by the Jaeb Center for Health Research to check best-corrected vision in children. Children 7 years of age or older will be tested using the electronic ETDRS option on the EVA system, while children younger than 7 years of age will be tested on the ATS-HOTV option. Refer to **MOP Section 6.3** for further details on refraction and visual acuity, including acceptable EVA alternative devices (e.g., M&S, VistaVision, Good-Lite).

Optical coherence tomography (OCT): Optical coherence tomography (OCT) is a diagnostic imaging technique that produces cross-sectional tomograms of the posterior segment eye structures. A computer algorithm determines the boundaries of the different layers of the retina and subsequently, retinal thickness and volume data are calculated. Spectral-domain (SD) OCT will be used in this study to monitor the effects of treatment by measuring changes in macular thickness. Heidelberg Spectralis SD-OCT unit, Zeiss Cirrus, and TopCon are the approved OCT imaging machines for study assessments. If there is more than one OCT machine at a site, an effort will be made to use the same machine each time for consistency in measurements. The OCT technician should capture one 20x20 High Speed Volume scan centered on the macula for both eyes at each visit. The study ophthalmologist should record central subfield thickness measurements from the thickness map and structural observations (subretinal fluid, cystoid spaces, epiretinal membrane) on **OCT Form**.

MRP8/14 serum levels: Blood will be drawn to measure MRP8/14 serum levels at Baseline, Month 6, Month 12, and Treatment Failure. See **MOP Section 6.5** for details on storage, transmission, and analysis of samples.

Blood for biobanking: Blood will be drawn at Baseline, Month 6, Month 12, and treatment failure and kept in biobank storage freezers at each site for future analysis in ancillary biomarker studies. See **MOP Section 6.5** for details on storage and transmission of blood samples.

Adalimumab antibody levels: Patients will have blood drawn to test for adalimumab antibody levels at Baseline, Treatment Failure (if applicable), Month 6, and Month 12. Following treatment failure, an

investigator may elect to have one additional sample collected outside of these pre-specified study visit time points if the sample is relevant to the patient's treatment plan. See **MOP Section 6.5** for details on transmission and analysis of samples.

Rectal swab: Patients will provide rectal swabs at baseline, Month 12, and Treatment Failure (if applicable) for gut microbiome and human transcriptomes analyses.

Monitoring for arthritis activity: Patients will be assessed for arthritis activity using the Juvenile Arthritis Disease Activity Score for 10 and 27 joints (JADAS-10 and -27) by a pediatric rheumatologist.

Quality-of-life questionnaires Quality of life will be measured at Baseline, Month 6, Month 12 and Treatment Failure visits. Health-related quality of life (HR-QOL) will be assessed in patients 5 years and older using the Child Health Assessment Questionnaire (CHAQ). The EuroQol 5 Dimension Youth Survey (EQ-5D-Y) will also be completed by patients 4 years and older. Both of these questionnaires can be taken by patients and their caretakers. Vision-related quality of life (VR-QOL) will be assessed in patients using the Children's Visual Function Questionnaire (CFVQ) for patients aged 3-7 years and the Effect of Youngster's Eyesight on Quality of Life (EYE-Q) questionnaire for patients 5 years and older.

8.2 SAFETY AND OTHER ASSESSMENTS

Review of adverse events: The study coordinator will review each item on **Adverse Event Checklist** with patients and their caregivers and record it on the CRF. The study coordinator will also record any adverse events that the study ophthalmologist or rheumatologist have observed during the study visit. See **Section 8** for further detail on classification and reporting requirements for adverse events.

Serum chemistry and complete blood count: Patients prescribed an antimetabolite will have their blood drawn for a complete blood count and serum chemistry panel approximately every 3 months, while patients not prescribed an antimetabolite will have these labs done every 6 months—this is standard of care. The 9-month blood draw for standard of care labs can be completed any time between month 8 and month 10 for patients who are taking an antimetabolite. The study coordinator will review the lab report and record values on **Standard of Care Lab Form**, which the CC will monitor for safety events when CRFs are submitted for data entry. **Adverse Event Checklist** and **Treatment Assessment Form** will guide study coordinators on when to report lab values that are out of reference range and constitute a lab safety event. Study teams will also order **tuberculosis screening** at the baseline visit, if the patient has not been tested within 12 months prior to enrollment. If the test comes back indeterminate, it should be repeated. If it comes back positive, and the patient does not have a history of treatment for latent tuberculosis, then the patient should be evaluated for the need for treatment.

Pregnancy test for women of reproductive age: Serum or urine pregnancy test will be administered at every study visit for women post menarche. Study coordinators are required to notify the CC via **Serious Adverse Event Narrative** in the event of a positive pregnancy test. See **Section 8.3.8** for details on pregnancy reporting.

Patient perception of randomized assignment: Prior to unmasking (either at Month 12 or at the treatment failure visit), patients will be asked which treatment group they believe they were randomized to and reason for their guess. The study coordinator will record this information on the **Treatment Assessment Form** and then the patient and their caregivers will be unmasked.

8.3 ADVERSE EVENTS AND SERIOUS ADVERSE EVENTS

8.3.1 DEFINITION OF ADVERSE EVENTS (AE)

Adverse event means any untoward medical occurrence associated with the use of an intervention in humans, whether or not considered intervention-related (21 CFR 312.32 (a)).

Examples* may include:

- Increased intraocular pressure (>24 mm Hg)
- Abnormal lab findings (≥ 2 times but < 5 times the upper limit of normal AST or ALT, rise in creatinine to ≥ 1.5 to < 2 mg/dL, reduction of white blood cell count to below 2500)
- Concurrent accident or illness
- Increase in the frequency and severity of symptoms of a pre-existing condition
- Side effects such as gastrointestinal upset, nausea, vomiting, fatigue

*Additional details on adverse event reporting are provided in the case report form: **Adverse Event Checklist**.

8.3.2 DEFINITION OF SERIOUS ADVERSE EVENTS (SAE)

An AE or suspected adverse reaction is considered "serious" if, in the view of either the investigator or sponsor, it results in any of the following outcomes: death, a life-threatening adverse event, inpatient hospitalization or prolongation of existing hospitalization, a persistent or significant incapacity or substantial disruption of the ability to conduct normal life functions, or a congenital anomaly/birth defect. Important medical events that may not result in death, be life-threatening, or require hospitalization may be considered serious when, based upon appropriate medical judgment, they may jeopardize the participant and may require medical or surgical intervention to prevent one of the outcomes listed in this definition.

Below is a list of thresholds for classifying lab values as non-serious and serious:

	Non-Serious Adverse Event	Serious Adverse Event
Leukocytes	$>1,000$ to $<2,500/\mu\text{L}$	$\leq 1,000/\mu\text{L}$
Platelets	$20,000 \geq$ to $\leq 75,000/\mu\text{L}$	$<20,000/\mu\text{L}$
Hemoglobin	≥ 6.5 to $< 9.0 \text{ g/dL}$	$<6.5 \text{ g/dL}$
SGOT (AST) or SGPT (ALT)	≥ 2 to < 5 times the upper limit of normal	≥ 5 times the upper limit of normal
Creatinine	≥ 1.5 to $< 2 \text{ mg/dL}$	$\geq 2 \text{ mg/dL}$

If a lab value surpasses the Non-Serious Adverse Event threshold, the patient must stop their study treatment (adalimumab or placebo), then may resume once levels are below the upper limit of normal. It is recommended to recheck labs weekly following the observation of the elevated lab value. If the lab value remains at the non-serious threshold for more than 28 days, it will be considered an SAE.

If lab values reach the Serious Adverse Event threshold, the patient will stop the study treatment and will not be eligible to restart treatment until the lab value no longer meets the Non-Serious Adverse Event threshold. Patients will continue to be followed through Month 12 regardless of whether or not they regain eligibility to start treatment.

If a patient also stops taking an antimetabolite due to elevated lab values, they are encouraged to restart the antimetabolite as soon as possible, when deemed safe by their provider.

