6.5.2 ANTIMETABOLITE THERAPY

If patients are on an antimetabolite (methotrexate, mycophenolate mofetil, azathioprine, or leflunomide) the dose and route of administration must be stable for at least 90 days prior to randomization in order to be eligible for the trial. Such patients will continue on their same dose and route of administration throughout the trial. The maximum allowable dose of methotrexate is 25 mg weekly in either oral or injectable form. The maximum allowable dose of mycophenolate mofetil is 3 g/daily. The maximum allowable dose of azathioprine is 250 mg daily and for leflunomide it is 20 mg

daily. The dose of azathioprine and leflunomide must also be stable for at least 90 days prior to enrollment. Note, the patient should not be on any other immunosuppressive agent.

The study will not provide antimetabolites. Treating physicians must continue to prescribe the concomitant therapy for patients during the trial. Treatment should be recorded on the Treatment Assessment Form.

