Discontinuation due to *intolerability*: Patients may discontinue their current treatment regimen due to side effects. Once side effects resolve, patients may restart their treatment regimen. Discontinuation for intolerance is NOT a treatment failure. Patients should still complete all study visits through Month 12.

Discontinuation due to *safety*: Patients who experience abnormal lab results meeting the designated threshold of an AE or other AEs such as an opportunistic infection will immediately stop taking both the study treatment and concomitant antimetabolite therapy if applicable. These AEs are often reversible. In the case of non-serious and serious lab AEs, patients may restart medication when the lab results have normalized. Discontinuation for safety reasons is NOT a treatment failure. Patients should still complete all study visits through Month 12. Patients who develop an illness, such as a febrile illness, $\geq 101^{\circ}\text{F}/38.3^{\circ}\text{C}$ or an infection requiring antibiotics, should consult their study physician regarding treatment and may stop taking the study medication and antimetabolite per investigator's discretion. Under the discretion of the investigator, patients should resume treatment as soon as it is determined to be safe. Note, patients should not stop treatment due to milder illnesses such as upper respiratory infections (colds). Additionally, patients who develop any of the following will also discontinue treatment according to the full prescribing information and labeling in the SmPC: serious infections,

opportunistic infections (including invasive fungal infections) or sepsis, Hepatitis B reactivation, new or worsening symptoms of congestive heart failure, or central or peripheral nervous system demyelinating disorders. If the investigator determines it is safe for the patient to restart treatment upon resolution of the disorder, the patient will restart.

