8.3.8 REPORTING OF PREGNANCY

Any pregnancy will be reported to the coordinating center within 24 hours of study personnel learning of the event. The patient should stop study treatment immediately. Patients taking concomitant immunomodulatory therapy should also stop this medication as they have potential teratogenic effects. Every effort should be made to follow up with the patient at the conclusion of the pregnancy to collect any information on congenital abnormalities or other complications.

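### Protocol 8.3.2's restart test after a non-serious laboratory event is already met by a low blood count when study drug is stopped

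*Protocol*

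**What the plan says.** Protocol 8.3.2 tabulates non-serious and serious ranges for leukocytes, platelets, hemoglobin, AST/ALT and creatinine. The first three are events on the low side, the last two on the high side. Two restart rules follow the table.

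- After a non-serious event, study treatment stops and the patient "then may resume once levels are below the upper limit of normal".
- After a serious event, the patient "will not be eligible to restart treatment until the lab value no longer meets the Non-Serious Adverse Event threshold".

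Between them stands a monitoring sentence, "It is recommended to recheck labs weekly following the observation of the elevated lab value", and a rule that a value staying in the non-serious range for more than 28 days becomes an SAE. On the antimetabolite, 8.3.2 says only that a patient who also stops it is "encouraged to restart the antimetabolite as soon as possible, when deemed safe by their provider".

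Section 7.1 covers the same events under discontinuation for safety. Patients "will immediately stop taking both the study treatment and concomitant antimetabolite therapy if applicable". It has one restart rule: "In the case of non-serious and serious lab AEs, patients may restart medication when the lab results have normalized". It does not define normalized, and neither section refers to the other. Section 6.5.2 says of patients on an antimetabolite: "Such patients will continue on their same dose and route of administration throughout the trial". Section 8.3.8 adds a further stop, for pregnancy: "Patients taking concomitant immunomodulatory therapy should also stop this medication as they have potential teratogenic effects".

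**The concern.** These are stop and restart instructions for a largely pediatric population on adalimumab, often with an antimetabolite. Section 2.3.1 lists leukopenia and thrombocytopenia among the risks of adalimumab, and leukopenia among those of methotrexate and mycophenolate, so low counts are foreseeable. An upper limit cannot signal recovery from a low count. The monitoring sentence, which speaks of an elevated value, suggests the paragraph was drafted with high values in mind.

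The two rules in 8.3.2 also appear to be in the wrong order for liver enzymes: the milder event seems to carry the stricter restart condition. Finally, a site working from 8.3.2 and 6.5.2 would not find there the antimetabolite stop that 7.1 orders. What is at stake is consistent dosing decisions across sites. No power, alpha or endpoint figure is involved.

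**Working it through.** The plan states no figure to reproduce. The check applies each rule to each row of the 8.3.2 table.

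**Step 1. Non-serious test, row by row.** The documents give no ULN values. I assume only that the ULN of each blood count lies above its low-side cut-off, and that the creatinine ULN is not above 1.5 mg/dL.

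| Analyte | Non-serious range | Side | Below ULN when drug is stopped? | Serious bar lifts at |
|---|---|---|---|---|
| Leukocytes | >1,000 to <2,500/µL | low | yes | ≥2,500/µL |
| Platelets | 20,000 to 75,000/µL | low | yes | >75,000/µL |
| Hemoglobin | 6.5 to <9.0 g/dL | low | yes | ≥9.0 g/dL |
| AST/ALT | 2 to <5 x ULN | high | no | <2 x ULN |
| Creatinine | 1.5 to <2 mg/dL | high | no | <1.5 mg/dL |

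Examples: leukocytes 2,000/µL, platelets 50,000/µL and hemoglobin 8.0 g/dL are all non-serious events and all below any plausible ULN. The test fails to discriminate in 3 of 5 rows. In those rows the serious bar does work and is stricter than the literal non-serious test, so there is no reversal for blood counts.

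**Step 2. AST/ALT, reading 8.3.2 alone.**

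- Fall from 3 x ULN (non-serious) to 1.5 x ULN: 1.5 is not below 1, so the patient waits.
- Fall from 6 x ULN (serious) to 1.5 x ULN: 1.5 is below 2, so the bar is lifted.

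The rules are reversed for values from 1 to <2 x ULN.

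**Step 3. The same case with 7.1 added, at 1.5 x ULN.**

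- If normalized means within the laboratory range, the patient waits after either event. A value in range is always below 2 x ULN, so it also satisfies the serious bar. Both sections can be followed and the reversal disappears.
- If normalized means out of the adverse event range, the patient may restart after either event. That conflicts with the non-serious test in 8.3.2. Footnote b to Section 5.2 may use normal in this sense, but it concerns eligibility.

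**Step 4. Creatinine.** The band in which 8.3.2 alone would allow restart after a serious but not a non-serious event is 1.5 − ULN. For assumed ULNs of 0.6, 0.9, 1.2 and 1.5 mg/dL:

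- 1.5 − 0.6 = 0.9 mg/dL
- 1.5 − 0.9 = 0.6 mg/dL
- 1.5 − 1.2 = 0.3 mg/dL
- 1.5 − 1.5 = 0 mg/dL

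**Step 5. Antimetabolite.** Section 7.1 makes the stop mandatory at the adverse event threshold. Section 8.3.2 orders only study treatment to stop and treats an antimetabolite stop as something that may have happened. Section 6.5.2 states continuation with no exception, although 7.1 and 8.3.8 each create one.

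**The case against.** The strongest reply is that 7.1 already governs. Its requirement that results have normalized works in both directions and covers serious and non-serious laboratory events alike. This stands in part. A reader might infer that sites had no restart test at all for low counts; the documents do not support that, because 7.1 supplies one. What remains is that 7.1 leaves the term undefined and 8.3.2 states a different, unusable test without pointing to it.

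On AST/ALT, the serious rule is worded as a bar, which is a necessary condition and not a permission. A value of 5 x ULN or more has also passed the non-serious threshold, so the below-ULN test can be read as still applying. It would therefore be too strong to call the reversal certain, or to say that 7.1 necessarily contradicts the serious rule: under the within-range reading of Step 3 it does not. The reversal is the plain reading of 8.3.2 by itself and no more.

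On the antimetabolite, not repeating an order does not cancel it, and the specific safety instructions in 7.1 and 8.3.8 can be read as exceptions to the general rule in 6.5.2. That is right, and it makes this part editorial.

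It can also be said that no clinician would restart at the moment of stopping, and that weekly rechecks and the 28-day SAE rule limit harm. Both are fair. Neither supplies a restart point; they leave judgement to fill a gap in a written rule.

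**Conclusion.** The non-serious restart test in 8.3.2 is wrong as written for leukocytes, platelets and hemoglobin, 3 of 5 rows, on the sole assumption that each ULN lies above the low-side cut-off. Read alone, 8.3.2 is also looser after a serious than after a non-serious AST/ALT event between 1 and <2 x ULN, unless the serious bar is combined with 7.1 or with the below-ULN test. The creatinine version depends on an assumed ULN.

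Severity is minor. Section 7.1 says that stopping for safety is not a treatment failure and that follow-up continues, and no effect on the primary analysis is claimed. The number of laboratory events is not in the documents, so the number of affected restart decisions cannot be stated. A reader might also infer that only patients still in follow-up after enrollment stopped on 14 February 2024 were exposed to the wording. That confuses two groups: the amendment history in Section 10.3 lists no change to 8.3.2, so the rule covered earlier participants too, while an amendment can reach only those still on treatment.

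**What to change.** In 8.3.2, replace the single non-serious test by one with a direction for each analyte:

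- Low counts: resume only on recovery to at least leukocytes ≥2,500/µL, platelets >75,000/µL and hemoglobin ≥9.0 g/dL. These are the edges of the existing non-serious ranges and match the exclusion cut-offs in Section 5.2.
- AST/ALT and creatinine: resume when below ULN.
- State that the serious-event bar applies in addition to this test, not in its place.

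In 7.1, define normalized by the same limits and refer to 8.3.2.

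Editorial cross-references: in 8.3.2, point to the antimetabolite stop in 7.1 and keep the existing encouragement to restart that drug promptly when the provider judges it safe. In 6.5.2, add the exceptions for a safety stop under 7.1 and for pregnancy under 8.3.8.

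The downside is that a patient whose AST/ALT usually sits between 1 and 2 x ULN may wait longer to restart after a serious event. Section 5.2 excludes only at 2 x ULN or above, so such patients could have enrolled. The cost is one wording amendment to 6.5.2, 7.1 and 8.3.2, with the IRB and ethics approval that the Statement of Compliance requires, and a note to sites. Sample size, endpoint and analysis do not change.
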